3.1.2. Secondary Immunogenicity Endpoints

- Seropositivity rate as determined by ELISA from approximately 3 years (38 months) to 10 years (118 months) after the first booster vaccination in Study 700401 and after the second booster vaccination in this study;
- Seropositivity is defined as $ELISA > 126$ VIE U/ml;
- Geometric mean antibody concentration (GMCs) as determined by ELISA from approximately 3 years (38 months) to 10 years (118 months) after the first booster vaccination in Study 700401 and after the second booster vaccination in this study;
- Geometric mean antibody titers (GMTs) as determined by NT from approximately 3 years (38 months) to 10 years (118 months) after the first booster vaccination in Study 700401 and after the second booster vaccination in this study;
- Geometric mean of fold increase (GMFR) as determined by ELISA from before booster to postbooster in this study;
- Geometric mean of fold increase (GMFR) as determined by NT from before booster to postbooster in this study.

3.2. Safety Endpoints

- Injection site reactions observed in the period from the second booster vaccination until the following blood draw;
- Systemic reactions observed in the period from the second booster vaccination until the following blood draw.

3.3. Baseline Variables

Age at first dose of primary vaccination, age at enrollment, age at second booster dose, gender, BMI, tick-bite history are considered as baseline variables. Age at first dose of primary vaccination (Study 209) will be categorized as 1-2, 3-6, 7-15, 12-15 years. Age at second booster dose will be based on vaccine dose-level (0.25 mL vs 0.5 mL).

Medical history and physical exam evaluated at Visit 1 of this current study are also considered as baseline variables.

4. ANALYSIS SETS

4.1. Full Analysis Set

An All-Enrolled Population will be defined as the Full Analysis Set, which consists of all subjects enrolled into the study. Any subjects who consented are included in the population. Subject disposition, history of tick bites, and demography will be presented for this population.

4.2. 'Per Protocol' Analysis Set

This analysis set is the primary analysis population for immunogenicity.

This Per-Protocol population includes subjects who:

1. Have been enrolled (consented) and meet all inclusion/exclusion criteria at all visits.
2. Have available assay results (ELISA or NT) at any blood sampling visit.
3. Have no other major protocol violations.

Above listed items 1 & 2 will be determined by computerized checks of the data, while item 3 will be determined by clinical review as these are considered as major protocol violations per the original protocol, which will eventually be entered into the database from Protocol Deviation (PD) case report form entries.

Subjects with major protocol deviations will be excluded from the primary analysis population, or in some instances, the ELISA and NT results affected by a protocol deviation at certain visit(s) will be excluded from the analysis.

If a subject meets the exclusion criterion 2, which is that subject has a history of infection with or vaccination against other flaviviruses (eg, Dengue fever, yellow fever, Japanese B encephalitis) since his/her first booster vaccination in Study 700401, the subject's affected ELISA results will be excluded from the analysis due to cross-reactivity. There is no cross-reactivity with the NT, so the NT results will be included in the analysis. The subject will be included in Per-Protocol population, under condition that he/she satisfies the rest of the conditions in above items 1 to 3.

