**Table 6.1-1**  
**Composition of TBE Vaccines**

Composition of a single dose	FSME-IMMUN 0.25 ml	FSME-IMMUN 0.5 ml
Formaldehyde-inactivated TBE virus	target 1.2 µg (range 1.00-1.38 µg)	target 2.4 µg (range 2.00 – 2.75 µg )
Origin of production virus seed	supernatant from chick embryo cells*	supernatant from chick embryo cells*
Aluminum hydroxide, hydrated	0.17 mg Al 3+	0.35 mg Al 3+
Human serum albumin	0.25 mg	0.5 mg
Sodium chloride	1.725 mg	3.45 mg
Disodium hydrogen phosphate	0.11 mg	0.22 mg
Potassium dihydrogen phosphate	0.023 mg	0.045 mg
Sucrose	max. 7.5 mg	max 15 mg
Formaldehyde	max. 2.5 µg	max. 5 µg
Protaminsulfate	max. 0.25 µg (in traces)	max. 0.5 µg (in traces)
Neomycin and Gentamicin	in traces	in traces
Water for injection	ad 0.25 ml	ad 0.5 ml

\* infected with working virus seed generated from chick embryo cells

Both FSME-IMMUN 0.25 ml Junior and FSME-IMMUN 0.5 ml are licensed for intramuscular injection. The vaccines will be administered in accordance with the Summary of Product Characteristics (SmPC): FSME-IMMUN 0.25 ml Junior is indicated for children and adolescents aged 1-15 years (until the last day before the 16th birthday) whereas FSME-IMMUN 0.5 ml has been approved for use in adults from 16 years of age (i.e. from the 16th birthday).

According to the current SmPC for FSME-IMMUN 0.25 ml Junior / FSME-IMMUN 0.5 ml, the first booster vaccination should be given at 3 years after completion of the primary vaccination series (which consists of 3 vaccinations). Subsequent booster vaccinations are recommended at 3 to 5 year intervals in children and adolescents as well as in adults up to 60 years of age.

The Sponsor will provide the Investigator with sufficient vaccine to conduct the study as well as the appropriate certificates of analysis for the investigational products.

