### 9.2 Exclusion Criteria

Subjects who participated in Study 700401 and meet ANY of the following criteria are not eligible for participation in this study:

- Subject received any TBE vaccination since his/her first booster vaccination in Study 700401;
- Subject has a history of infection with or vaccination against other flaviviruses (e.g., Dengue fever, yellow fever, Japanese B encephalitis) since his / her first booster vaccination in Study 700401;
- Subject is known to be HIV positive (a special HIV test is not required for the purpose of the study) since his/her first booster vaccination in Study 700401;
- Subject received a blood product or immunoglobulins within 90 days before any blood draw or in the period between the blood draw and the booster vaccination (as applicable);
- Subject has a known or suspected problem with drug or alcohol abuse (> 4 liters of wine/week or equivalent level of other alcoholic beverages);
- Subject / parent(s) / legal guardian(s) is / are in a dependent relationship with the study investigator or with a study team member. Dependent relationship includes close relatives (i.e., children or grandchildren, partner / spouse, siblings) as well as employees of the Investigator or the site conducting the study.

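### As written, SAP 4.2 item 1 lets a first eligibility breach after Visit 1 remove a subject's earlier, unaffected titres from the primary set, and the SAP does not say when its result-level exclusion applies instead

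*SAP*

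**What the plan says.** SAP 4.2 defines the per-protocol set and states its role: "This analysis set is the primary analysis population for immunogenicity". Item 1 requires that subjects "Have been enrolled (consented) and meet all inclusion/exclusion criteria at all visits". Item 1 is not left to clinical judgement: "Above listed items 1 & 2 will be determined by computerized checks of the data". Protocol 13.2 asks only that the criteria be fulfilled. The extension to all visits comes from the SAP.

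Two further statements in SAP 4.2 qualify the rule:

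- Subjects with major deviations are excluded, "or in some instances, the ELISA and NT results affected by a protocol deviation at certain visit(s) will be excluded from the analysis". The instances are not listed.
- A subject who meets exclusion criterion 2 (another flavivirus infection or vaccination) stays in the set. Only the affected ELISA results are dropped and NT is kept, provided that the remaining conditions of items 1 to 3 are met.

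SAP 6.4.4.1 repeats whole-subject exclusion for failing the criteria, under a heading about deviations before enrollment. SAP 6.4.4.2 sends post-enrollment deviations to medical or clinical review.

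Protocol 10.3.2 and Table 20.2-1 have the criteria reviewed at every persistence draw and at the booster visit. At least two can be breached for the first time years after entry (Protocol 9.2). One is any TBE vaccination since the first booster. The other reads "Subject received a blood product or immunoglobulins within 90 days before any blood draw".

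**The concern.** Take a subject who first breaches a criterion at Month 106. An off-study TBE vaccination shortly before that draw cannot have changed the titres from Month 38 to Month 94, yet item 1 removes them all from the primary analysis. Such a vaccination is plausible, since Protocol 6.1 reports that "Subsequent booster vaccinations are recommended at 3 to 5 year intervals in children and adolescents". Protocol 9.5 and 10.6 say that data collected up to withdrawal or discontinuation will be used in the analysis, which fits poorly with dropping them from the primary set.

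The rule also makes membership at Month 38 depend on what happens later. Subjects with low titres are invited for the booster and leave the persistence schedule. Subjects with lasting antibody return for up to eight draws and are checked each time. If the breach risk per check is roughly constant, the rule removes persisters more often, and the early seropositivity rates in the primary analysis are pulled down.

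**Working it through.** **The plan's own figure.** Protocol 13.1 states that with about 175 subjects the 95% confidence interval extends no more than 5.8 points from an observed rate near 90%. Clopper-Pearson limits (SAP 5.2.3) give a largest distance of 5.38 points for 158/175 (90.3%) and 5.76 for 154/175 (88.0%). The stated bound holds.

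**Exposure to the rule.** Let q be the breach risk per check and k the number of checks. The chance of exclusion is 1 − (1 − q)^k. The documents give no q, so it is an assumption, with independent checks.

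| q | k = 2 (Visit 1 and Visit 4) | k = 8 (all persistence draws) |
|---|---|---|
| 0.5% | 1.0% | 3.9% |
| 1% | 2.0% | 7.7% |
| 2% | 4.0% | 14.9% |

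A subject with eight checks is about four times as likely to be removed as one with two.

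**Effect at Month 38.** Further assumptions: true rate 90%, n = 175, 2 checks for seronegative subjects and 6 on average for seropositive subjects.

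- Observed rate = 0.9(1 − q)^6 / [0.9(1 − q)^6 + 0.1(1 − q)^2]
- Retained n = 175 × [0.9(1 − q)^6 + 0.1(1 − q)^2]

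| q | 0.9(1 − q)^6 | 0.1(1 − q)^2 | Rate | Retained n |
|---|---|---|---|---|
| 0.5% | 0.8733 | 0.0990 | 89.82% | 170 |
| 1% | 0.8473 | 0.0980 | 89.63% | 165 |
| 2% | 0.7973 | 0.0960 | 89.25% | 156 |

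The downward shift is 0.18, 0.37 and 0.75 points. With 8 checks instead of 6 for seropositive subjects it is 0.27, 0.56 and 1.15 points.

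**Part of the loss is legitimate.** A breach at Visit 1 should exclude the subject. That accounts for 175q: 0.9, 1.75 and 3.5 subjects out of 4.8, 9.6 and 18.7 lost. About 4, 8 and 15 are recoverable. The shift in the rate is unchanged, because the Visit 1 factor (1 − q) cancels.

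**Precision.** At about 90% the largest distance is 5.53 points for n = 170, 5.68 for n = 165 and 5.86 for n = 156 (140/156). Only the last exceeds 5.8, and barely.

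**Draws lost per eight-draw subject.** The rule as written loses 8[1 − (1 − q)^8] draws on average: 0.31, 0.62 and 1.19. Dropping results only from the breach onward loses the sum of 1 − (1 − q)^k over k = 1 to 8: 0.18, 0.35 and 0.69. The difference, about 0.14, 0.27 and 0.51 draws, is earlier data needlessly removed.

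**The case against.** The best defence is that SAP 4.2 already contains a result-level route. Item 3 speaks of other major violations, which suggests that item 1 breaches are major violations too, so the sentence stating that "the ELISA and NT results affected by a protocol deviation at certain visit(s) will be excluded from the analysis" could reach them. SAP 6.4.4 can be read the same way: whole-subject exclusion sits under deviations before enrollment, and later deviations go to clinical review. The SAP revision history says that 4.2 was aligned with a protocol deviation plan. That plan is not among the documents and may list the visit-level cases.

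This stands as a possible reading, and it means that deletion of earlier titres is not certain. It does not settle the matter. Item 1 is applied by computer check, the SAP nowhere says that the result-level sentence overrides it, and the criterion 2 carve-out still requires the rest of items 1 to 3.

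Four stronger readings are tempting, and the documents do not support them:

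- *Every criterion acts on the whole subject.* Criterion 2 does not, and NT, the primary-endpoint assay, is kept there.
- *The titres are lost to the study.* They stay in the mITT set (SAP 4.4.1), in which the primary endpoint is also analysed (SAP 6.1). At Month 38 neither set extrapolates, so the comparison is free of that difference. From Month 58 it is not, because mITT also drops extrapolation. The reverse cumulative curves and the logistic regression have no mITT version.
- *The bias is established.* It needs a roughly constant breach risk per check, and no rate is given. The six-check average is also an assumption: boosting is triggered at NT ≤ 20 and/or ELISA ≤ 126 VIE U/ml, so some seropositive subjects leave early.
- *Every earlier result is valid.* A condition detected late, such as HIV infection, may bear on earlier draws.

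**Conclusion.** The point holds as a defect of specification in the primary analysis set. Read as written, item 1 removes earlier titres that a first breach after Visit 1 could not have affected, for any criterion other than number 2, and the SAP does not say when the milder result-level rule replaces it.

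The direction of the selection follows from the design, if breach risk per check is roughly constant. Its size is conditional: 0.2 to 0.4 points at Month 38 for 0.5% to 1% per check and 0.75 points at 2%, under the 90% rate and the 2-versus-6 checks assumed above. This is small beside an interval that may extend 5.8 points, and precision changes little. The change is worth making because it is cheap, concerns the primary set, and follows what the SAP already does for criterion 2.

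**What to change.** In SAP 4.2:

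- Assess the inclusion/exclusion criteria at Visit 1 for per-protocol membership.
- For a first breach after Visit 1, exclude results from the breach onward.
- For the 90-day blood product or immunoglobulin criterion, exclude only the affected draw.
- Keep the criterion 2 rule as it stands.
- Let clinical review exclude earlier draws where a condition detected late may have affected them.

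State whether results removed after a breach are left missing or extrapolated. SAP 5.2.1 now names only early withdrawal and second booster as reasons for estimation, so the answer is open, and a subject discontinued because of a breach might be treated as an early withdrawal.

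Reconcile the new text with SAP 6.4.4.1, 6.4.4.2 and the protocol deviation plan, and report the number of subjects and results excluded by visit.

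The cost is SAP wording and a visit-level flag in programming. The per-protocol denominator will vary by visit and must be shown in each table.

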4.3. Safety Analysis Set

The safety population will include any subjects who received the second booster dose in this study.

4.4. Other Analysis Sets

4.4.1. mITT Population

All enrolled subjects who have assay results (ELISA or NT) available at any blood sampling visit in this study will be included in the modified intent-to-treat (mITT) population. This analysis set is for the immunogenicity analysis purpose. This population will be used as the secondary analysis population for other immunogenicity objectives. All available assay results will be included in this analysis set.

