## 10.4 Medications and Non-Drug Therapies

The following medications are **not** permitted:

- any blood products or immunoglobulins - within 90 days before each blood draw, in the period between the blood draw and the second booster vaccination, and from the second booster vaccination until the Post-booster Visit;
- any treatment that can be expected to influence immunological functions (e.g., systemic corticosteroids) – within 30 days prior to the second booster vaccination until the Post-booster Visit.  
A subject who has taken any of these medications within the time frames specified above before administration of the second booster vaccination will be excluded / discontinued from this study. Administration of these medications between the second booster vaccination and the Post-booster Visit will be considered a protocol deviation;
- any live or inactivated vaccine given within 4 weeks or 2 weeks, respectively, before the second booster vaccination, until the Post-booster Visit.  
Any vaccination (except if given in medical emergencies such as tetanus or rabies infection) will be considered a protocol deviation.

The following medications and procedures will **delay** the booster vaccination:

- antipyretics received within 4 hours prior to the scheduled time of vaccination
- any live or inactivated vaccine received within 4 or 2 weeks before the booster vaccination, respectively.
- donation of blood, blood fractions or plasma within 30 days prior to the scheduled booster vaccination. Subjects are further requested to refrain from donation of blood, blood fractions and plasma until the Post-booster Visit (Visit 5).

For further details on Delay Criteria refer to Section [9.4](#).

Usage of any other medications or non-drug therapies is not restricted.

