5.2.2.2. GMT

To estimate the antibody response from approximately 3 years to 10 years after the first booster vaccination (from precedent study 700401), NT titers and ELISA concentrations measured at each blood sampling time point (including extrapolated from regression model for subjects with booster dose or early withdrawals from [Section 5.2.2.1](#), and the available assay results) after the first booster will be logarithmically transformed for analysis and GMTs/GMCs will be computed with 95% CI for each assay. The analysis will be applied to the [‘Per Protocol’ Analysis Set](#). For the [mITT Population](#), GMTs/GMCs with 95% CI will be computed using all available NT titers and ELISA concentrations, ie, no extrapolation from regression model will be done for subjects with booster dose or early withdrawals.

To estimate the antibody response after the second booster vaccination within this current study, NT titers and ELISA concentrations measured at the postbooster visit will be logarithmically transformed for analysis and GMTs/GMCs will be computed with 95% CI for each assay. The analysis will be applied to both the [‘Per Protocol’ Analysis Set](#) and [mITT Population](#). Data will be presented for each year, as well as for the combined postbooster.

The 2-sided, 95% confidence intervals for the GMTs/GMCs will be constructed by back transformation of the confidence intervals for the mean of the logarithmically transformed titers or concentrations computed using the Student t distribution.

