5.2.3. Analyses for Binary Data

All of the binary endpoints will be descriptively summarized along with the exact 2-sided 95% confidence interval (or Clopper-Pearson confidence limit) for the proportion. The exact confidence interval for proportion will be computed using the F distribution. If r equals the number of responses and n equals the number of subjects, then it follows that $p = r / n$ is the estimate of the proportion of responses. An exact 95% confidence interval can be computed by solving the following 2 equations. For the lower limit p_L , use:

$$p_L = \frac{rF_L}{(rF_L + (n - r + 1))} \text{ and for the upper limit } p_U, \text{ use } p_U = \frac{(r + 1)F_U}{(n - r) + (r + 1)F_U}$$

where F_L is the quantile from the F distribution for $\alpha=0.025$, with numerator degrees of freedom equal to $2r$ and denominator degrees of freedom equal to $2(n-r+1)$. F_U is the quantile from the F distribution for $\alpha=0.975$, with numerator degrees of freedom equal to $2(r+1)$ and denominator degrees of freedom equal to $2(n-r)$. When r equals 0, F_L should be set equal to 1.0 so p_L equals 0. When r equals n , F_U should be set equal to 1.0 so p_U equals 1. The confidence interval using the F distribution is described in Collett (1991¹) and implemented in SAS procedure (ie, PROC FREQ).

To estimate the seropositivity rate as determined by NT from approximate 3 years to 10 years after the first booster vaccination (from precedent study 700401), the proportion of subjects with $NT \geq 10$ at each blood sampling time point (including extrapolated from regression model for subjects with booster dose or early withdrawals from [Section 5.2.2.1](#), and the available assay results) after the first booster will be summarized with the exact 95% CI. Similarly, the proportion of subjects with $ELISA > 126$ at each blood sampling time point (including extrapolated results) after the first booster will be summarized with the exact 95% CI. The analysis will be applied to '[Per Protocol](#)' Analysis Set. For [mITT Population](#), which will include all available NT titers and ELISA concentrations, ie, no extrapolation from regression model will be done for subjects with booster dose or early withdrawals.

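### ELISA results excluded from the per-protocol analysis for flavivirus cross-reactivity stay in the mITT analysis, because SAP 4.4.1 makes no exception for them

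*SAP*

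**What the plan says.** SAP 4.2 (per-protocol set) deals with subjects who meet exclusion criterion 2, that is, infection with or vaccination against another flavivirus since the first booster. For them, "the subject's affected ELISA results will be excluded from the analysis due to cross-reactivity". The next sentence keeps the other assay: "There is no cross-reactivity with the NT, so the NT results will be included in the analysis". The subject stays in the per-protocol population if the remaining conditions are met.

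SAP 4.4.1 (mITT) admits every enrolled subject with an ELISA or NT result at any blood draw. On its role it says: "This population will be used as the secondary analysis population for other immunogenicity objectives". On the values it uses it says: "All available assay results will be included in this analysis set".

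The methods sections follow the same line. For GMTs and GMCs, SAP 5.2.2.2 has mITT computed "using all available NT titers and ELISA concentrations, ie, no extrapolation from regression model will be done". For seropositivity, SAP 5.2.3 describes mITT as a set "which will include all available NT titers and ELISA concentrations, ie, no extrapolation from regression model will be done". SAP 5.2.2.3 applies the GMFR to both sets without saying which values enter, so for GMFR the inclusion rule is the one in 4.4.1. SAP 6.2 confirms that GMCs and GMFRs are summarized in both sets.

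**The concern.** The per-protocol exclusion in 4.2 does not penalise poor adherence. The subject and the NT results remain, and only the ELISA values go, because of what the assay picks up after exposure to a related virus. That reason does not depend on the analysis set. A value set aside as cross-reactive in one set is no better a measure of TBE antibody in the other, and the SAP gives no reason for treating it differently.

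What is at stake is the mITT version of the secondary ELISA endpoints. A cross-reactive signal adds to the reading, so it makes ELISA persistence look better, which is the flattering direction in a persistence study. It would also add a cause to any ELISA difference between the two sets that has nothing to do with the other protocol deviations.

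The situation is foreseeable. Scheduled follow-up runs from month 38 to month 118. Protocol 10.4 limits other vaccines only around the second booster. Other flavivirus exposure is an exclusion criterion in Protocol 9.2, but SAP 4.2 itself provides for subjects who meet it and stay in the analysis.

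**Working it through.** **1. The rules side by side.**

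| | NT after other flavivirus exposure | ELISA after other flavivirus exposure |
|---|---|---|
| Per-protocol (SAP 4.2) | kept | affected results removed |
| mITT (SAP 4.4.1, 5.2.2.2, 5.2.3) | kept | kept: no exception stated |

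The only mismatch is in the ELISA column.

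**2. Inputs.** The plan gives no figure for this effect, so there is none to reproduce. Not in the documents, and assumed here as ranges:
- k, the number of affected results at a visit
- f, the fold rise in an affected result
- p, the true ELISA-positive proportion

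N = 175 is the expected number of participants in Protocol 13.1. N = 50 is an assumed late visit; numbers fall because the visits after Visit 1 apply only to subjects not yet boosted.

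**3. GMC.** If k of N values are each multiplied by f, the GMC is multiplied by f^(k/N).
- N = 175, smallest case: 2^(1/175) = 1.004.
- N = 175, largest case: 10^(10/175) = 1.141.
- N = 175, f = 4: 1.008 (k = 1), 1.040 (k = 5), 1.082 (k = 10).
- N = 50, k = 1 to 5, f = 2 to 10: 2^(1/50) = 1.014 to 10^(5/50) = 1.259.

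**4. Seropositivity rate.** Suppose all k affected results read above 126 VIE U/ml and the affected subjects are otherwise like the rest. Then k(1 − p) of them are expected to be false positives, and the rate rises by k(1 − p)/N.
- N = 175, p = 0.90: 0.06 points (k = 1), 0.29 (k = 5), 0.57 (k = 10).
- N = 175, k = 10, p = 0.80: 10 × 0.20/175 = 1.14 points. With p = 1.00 the rise is zero.
- Ceiling, if every affected subject is truly negative: k/N = 0.57 points (k = 1) to 5.71 points (k = 10).
- N = 50, k = 1 to 5, p = 0.80 to 1.00: 0 to 2.0 points; ceiling 2 to 10 points.

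As a yardstick, Protocol 13.1 promises a 95% interval extending at most 5.8 points from a rate near 90%. The exact interval at 157/175 (89.7%) extends 5.48 points down and 4.07 up, so that bound holds. Even with every affected subject truly negative, about 0.058 × 175 ≈ 10 of them would be needed to shift the rate by that much.

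**5. GMFR.** If k of N pre-booster values are raised f-fold and the post-booster values are not, the GMFR is multiplied by f^(−k/N). With N = 50, k = 1 and f = 2 to 10, that is 1/1.014 = 0.986 to 1/1.047 = 0.955. If the post-booster value is raised too, the two partly or wholly cancel.

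**6. Other differences between the sets.** SAP 5.2.1 leaves missing values at months 38 and 46 unestimated. From month 58, the per-protocol analysis extrapolates values for boosted or withdrawn subjects with at least three data points; mITT does not. Low antibody triggers the booster, so the observed values in mITT at later visits tend to come from subjects with higher antibody. That moves mITT ELISA in the same direction as cross-reactivity.

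**The case against.** The best defence is that mITT is meant to be an all-data set. Protocol 13.2 defines it only by available serology data, SAP 4.4.1 calls it secondary, and the primary endpoint is NT in the per-protocol set, where the affected ELISA values are already gone. In 5.2.2.2 and 5.2.3, the reference to all available results is explained as meaning no extrapolation, so it may never have been aimed at cross-reactive values. Other flavivirus exposure is an exclusion criterion reviewed at the blood-draw and booster visits, so cases should be few. Vaccinations must be recorded in the CRF (Protocol 12.3.2) and nonstudy vaccinations are listed (SAP 6.4.3), so nothing is hidden.

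Most of this stands, and it limits the size and importance of the point. It does not remove the mismatch. Protocol 13.2 decides which subjects enter mITT, not whether a cross-reactive reading counts as TBE antibody. The gloss on extrapolation suggests an oversight, but the unqualified sentence in 4.4.1 would still be programmed as written. A listing shows the exposure without correcting the estimate.

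It is also fair to say that the fix does not make the two sets cleanly comparable: from month 58 the difference in extrapolation remains.

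**Conclusion.** The point holds as an inconsistency with a conditional effect. As written, mITT keeps ELISA values that 4.2 excludes for cross-reactivity. If any subject is affected, the mITT ELISA rates and GMCs are biased upward and a raised pre-booster value lowers the GMFR. If none is affected, there is no bias. On the assumed ranges (1 to 10 of 175, 2- to 10-fold), the GMC ratio is about 1.004 to 1.14. The rate changes little when nearly all subjects are truly positive, a situation SAP 6.2 allows for by planning for no ELISA-negative subject. Small late visits are the most exposed. NT results and the primary per-protocol analysis are not touched, so the priority is low.

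A reader might infer more, and the documents do not support it:
- *That the SAP declares these results invalid and keeps them on purpose.* It says only that they are excluded because of cross-reactivity. Version 1.1 revised both the per-protocol and mITT text, but the revision history gives no reason for the mITT change.
- *That the mITT ELISA results are in fact biased.* No affected subject or value is reported.
- *That mITT is useless as a check.* The SAP does not present it as a sensitivity check on the assay, its NT results are sound, and an all-data set can show what the exclusions do.

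**What to change.** In SAP 4.4.1, replace the unqualified inclusion sentence with one to this effect: *mITT includes all available NT results, and all available ELISA results except the affected results identified under 4.2.* Carry the rule through to the ELISA seropositivity rates, GMCs and GMFRs in 5.2.2.2, 5.2.2.3 and 5.2.3. List the excluded values and give the number affected at each visit. Because 4.2 does not say which visits count as affected or for how long after exposure, the same list of affected results should be used for both sets.

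If the sponsor prefers to keep an all-data mITT, an acceptable alternative is to report the mITT ELISA results with and without the affected values, again with the number affected per visit.

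The cost is one SAP sentence and a few ELISA values fewer in mITT. No new data are needed, since the affected results must be identified for the per-protocol analysis anyway.
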